9.3.4. Outcomes

The primary outcomes are:

- **Stroke and systemic embolism (SE)** will be defined as a hospitalisation with one of the two following primary diagnoses:
 - ✓ Ischemic or undefined stroke (Giroud 2015),
 - ✓ Other systemic arterial embolism or surgical procedure for systemic arterial embolism.
- **Major bleeding**, based on International Society on Thrombosis and Haemostasis definition (Schulman 2005) and modified* to take into account the availability of information in the database, will be defined as a hospitalisation with one of the three following primary diagnoses:
 - ✓ Haemorrhagic stroke,
 - ✓ Other critical organ or site bleeding (intrapinal, intraocular, retroperitoneal, intraarticular or pericardial, or intramuscular),
 - ✓ Other bleeding with a transfusion during hospital stay, or resulting in death,

* Causes of death and haemoglobin result are not available to take into account not hospitalized fatal bleeding and bleeding causing a fall in haemoglobin level of 20g/l.
- **Clinically relevant bleeding (CRB)** will be defined as a hospitalisation with one of the five following primary diagnoses:
 - ✓ Haemorrhagic stroke,
 - ✓ Other critical organ or site bleeding (intrapinal, intraocular, retroperitoneal, intraarticular or pericardial, or intramuscular),
 - ✓ Gastro-intestinal bleeding,
 - ✓ Urogenital bleeding,
 - ✓ Other bleeding (ICD-10 codes in annex 1).
- **Death** defined as all-cause death (cause of death not available in the database).
- **Acute coronary syndrome (ACS)** will be defined as a hospitalisation with one of the two following primary diagnoses (Bezin 2015):
 - ✓ Myocardial infarction (MI),
 - ✓ Unstable angina.

9.3.5. Potential confounding

The potential confounders considered will be:

- **Gender and age** at index date;
- **CHA₂DS₂-VASc score** (Lip GY 2010) at index date, modified to take into account the availability of information in the database, and defined as the sum of points from following stroke risk factors: congestive heart failure (+1), hypertension (+1), age ≥ 75 years (+2), diabetes mellitus (+1), stroke or transient ischemic attack (TIA) history (+2), vascular disease history (+1), age 65-74 years (+1), female gender (+1), within tree-year database history;
- **CHADS₂ score** (for descriptive analysis, Waterman 2001) at index date, modified to take into account the availability of information in the database, and defined as the sum of points from following stroke risk factors: congestive heart failure (+1), hypertension (+1), age ≥ 75 years (+1), diabetes mellitus (+1), stroke or transient ischemic attack history (+2);
- **HAS-BLED score** (Pisters 2010, Lip GY 2011), modified to take into account the availability of information in the database, and defined as the sum of points from bleeding risk factors: hypertension (+1), abnormal renal function (+1), abnormal liver function (+1), stroke history (+1), bleeding history (+1), age > 65 years (+1), drug predisposing to bleeding (+1), within tree-year database history;

- **High dimensional Propensity Scores (hdPS)**: the probability to be treated by one of the studied drugs (rivaroxaban versus VKA, rivaroxaban versus dabigatran), will be estimated using hdPS taking into account all information of the database, with multiple data dimensions from subjects and disease characteristics, other LTD, other comorbidities using one-year history of hospitalisation (primary, linked, or associated diagnosis), three-year history of number of systemic drugs dispensed by therapeutic class (ATC 3 digit, including antacids A02A and drugs for peptic ulcer A02B) and of healthcare reimbursements (number of GP visits, specialist visits, emergency room visits, days of hospitalisation, nurse care and lab tests).
- **Drug predisposing to bleeding** during drug exposure: ASA, NSAIDs, antiplatelet agent and heparin or LMWH.

9.3.6. Healthcare resources

Healthcare resources use will be described from reimbursed claims and hospitalisation information, and classified as:

- Cardiovascular hospitalisations defined as all hospitalisations with cardiovascular primary diagnosis or diagnosis-related group of cardiovascular disease,
- Non-cardiovascular hospitalisations defined as all hospitalisations other than those defined above,
- Medical visits and technical acts,
- Cardiovascular and antidiabetic drugs reimbursed,
- Non-cardiovascular/antidiabetic drugs reimbursed,
- Lab tests,
- Products and services,
- Nursing acts,
- Physiotherapy acts,
- Transports,
- Sick leave daily allowances, disability allowances, pension,
- Other medical resources.

Healthcare resources related to AF will be:

- Specific Hospitalisations: Hospitalisations with primary diagnosis of AF, or cardioversion, or catheter ablation procedure, or stroke or systemic embolism, or CRB,
- Specific drugs: DOAC, VKA, beta-blockers, amiodarone, dronedarone, other antiarrhythmics,
- Specific lab tests: INR, haemostasis tests, creatinine, creatinine clearance, ALAT, ASAT, including sampling,
- Specific medical visits: cardiologist visit, other medical visits with date corresponding to the date of prescription of specific drugs or lab tests, neurologist visit after stroke event,
- Specific transport: Transport with date corresponding to the date of a specific hospitalisation, medical visit, medical procedure, or lab test.

Healthcare resources cost will be estimated using the French HAS methodological guide for economic evaluations (2011):

- From a societal perspective using diagnosis-related group (DRG) cost for hospitalisations and total cost for other healthcare resources.
- From the French healthcare insurance perspective using stay-related group (STG) cost for hospitalisations and reimbursed cost for other healthcare resources.

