- High dimensional Propensity Scores (hdPS) at index date for the probability of being treated by one of the studied drugs (rivaroxaban versus VKA, rivaroxaban versus dabigatran),
- Drug predisposing to bleeding during drug exposure: ASA, NSAIDs, antiplatelet agent and heparin or LMWH.

Healthcare resources

- Cardiovascular hospitalisations: Hospitalisations with primary diagnosis or diagnosis-related group of cardiovascular disease,
- Non-cardiovascular hospitalisations: Hospitalisations other than those defined above,
- Medical visits and technical acts,
- Cardiovascular and antidiabetic drugs reimbursed,
- Non-cardiovascular/antidiabetic drugs reimbursed,
- Lab tests,
- Products and services,
- Nursing acts,
- Physiotherapy acts,
- Transports,
- Sick leave daily allowances, disability allowances, pension,
- Other medical resources.

Healthcare resources related to AF

- Specific Hospitalisations: Hospitalisations with primary diagnosis of AF, or cardioversion, or catheter ablation procedure, or stroke or systemic embolism, or CRB,
- Specific drugs: DOAC, VKA, beta-blockers, amiodarone, dronedarone, other antiarrhythmics,
- Specific lab tests: INR, haemostasis tests, creatinine, creatinine clearance, ALAT, ASAT, including sampling,
- Specific medical visits: cardiologist visit, other medical visits with date

corresponding to the date of prescription of specific drugs or lab tests, neurologist visit after stroke event,

- Specific transport: Transport with date corresponding to the date of a specific hospitalisation, medical visit, medical procedure, or lab test.

Healthcare resources cost

- From a societal perspective: Diagnosis-related group cost for hospitalisations and total cost for other healthcare resources.
- From the French healthcare insurance perspective: Stay-related group cost for hospitalisations and reimbursed cost for other healthcare resources.

DATA SOURCES

The SNIIRAM database is the national healthcare insurance system database with individual anonymous information on all reimbursed outpatient claims linked to the national hospital-discharge summaries database system (PMSI) and the national death registry. It currently includes more than 96% of the French population of 65 million persons. To the extent that the SNIIRAM is a national database, all subjects are followed-up until they died, or for some people until they leave the country to live abroad. It contains individual anonymised information on:

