8. RESEARCH QUESTION AND OBJECTIVES

The research question is to assess the one-year and two-year benefit-risk of rivaroxaban for SPAF compared to VKA and dabigatran among new anticoagulant users.

The main study objective is to compare the one-year and two-year risk of each of the following individual outcomes: Stroke and systemic embolism (SE), major bleeding and death between new users of anticoagulant for SPAF during drug exposure: rivaroxaban versus VKA, and rivaroxaban versus dabigatran.

Secondary objectives are:

- To describe the drug exposure to rivaroxaban, dabigatran, and VKA for SPAF in new users, as well as pattern of use;

¹ Agence Nationale de Sécurité du Médicament et des produits de santé (French Medicines Agency)

² Caisse Nationale de l'Assurance Maladie des Travailleurs Salariés (French National Health Insurance Fund for Salaried Workers)

- To compare the one-year and two-year risk of the following individual outcomes: a composite of stroke and SE, major bleeding and death, clinically relevant bleeding (CRB) and acute coronary syndrome (ACS) between new users of anticoagulant for SPAF during drug exposure: rivaroxaban versus VKA, and rivaroxaban versus dabigatran;
- To estimate the cumulative incidence and the incidence rate of each individual main and secondary outcome (stroke and SE, major bleeding, CRB, death, composite criteria, and ACS), as well as according individual diagnose of each of these outcomes, during drug exposure for rivaroxaban, dabigatran, and VKA;
- To estimate the cumulative incidence of each individual main and secondary outcome (stroke and SE, major bleeding, CRB, death, composite criteria, and ACS), as well as according individual diagnose of each of these outcomes during post-anticoagulant exposure for rivaroxaban, dabigatran, and VKA (i.e. after anticoagulant discontinuation);
- To assess outcome risk factors, including (but not limited to), gender, age, stroke and bleeding risk scores (CHA₂DS₂-VASc and HAS-BLED), low or high dosage at index date for DOAC, drug predisposing to bleeding during drug exposure and significant baseline characteristics;
- To describe and compare healthcare resources utilisation related to SPAF during rivaroxaban, dabigatran, and VKA exposure, including outcomes, and their related costs from the societal perspective and from the French healthcare insurance perspective.

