9.7.2. Healthcare resources and cost

Healthcare resources and cost will be described for all and matched subjects according to the treatment group (rivaroxaban, dabigatran, VKA) during the first year of follow-up for all patients, and during two years of follow-up for those included in 2013. Comparison (rivaroxaban versus VKA, and rivaroxaban versus dabigatran) will be done for matched cohorts.

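### The cost labelled societal values neither lost production nor unpaid care, and its all-resource version also counts cash transfers, so it cannot support a statement about cost to society.

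*Protocol*

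**What the plan says.** Section 8 of the protocol sets a secondary objective to describe and compare resource use related to stroke prevention in AF, with "their related costs from the societal perspective and from the French healthcare insurance perspective".

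Section 9.3.6 then fixes how these costs are built. Its opening line gives the source: "Healthcare resources use will be described from reimbursed claims and hospitalisation information, and classified as". The general list that follows covers hospital stays, visits and acts, drugs, laboratory tests, nursing, physiotherapy, transport and similar items. One of its categories is "Sick leave daily allowances, disability allowances, pension". A second, shorter list covers AF-related resources only: specific stays, drugs, laboratory tests, visits and transport.

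The two perspectives are defined as follows:

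- Societal: "From a societal perspective using diagnosis-related group (DRG) cost for hospitalisations and total cost for other healthcare resources". The abstract has the same definition: "From a societal perspective: Diagnosis-related group cost for hospitalisations and total cost for other healthcare resources".
- Insurance: "From the French healthcare insurance perspective using stay-related group (STG) cost for hospitalisations and reimbursed cost for other healthcare resources".

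The section headed Healthcare resources and cost (the second one numbered 9.7.2) says: "Healthcare resources and cost will be described for all and matched subjects according to the treatment group". It limits comparisons between drugs to the matched cohorts and does not say which of the two lists it uses.

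**The concern.** A societal perspective differs from a payer's in what it counts. Cash allowances and pensions move money from the insurer to the patient. They are a real outlay for the insurer, but they consume nothing when society is taken as a whole. A societal account counts instead the production lost when people are absent from work, leave it early or die early, together with the time of unpaid carers.

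The protocol's first perspective includes the transfers, through the general list, and has no place for the other items. The comparison of costs under two named perspectives is a stated objective, so a report could conclude that one anticoagulant costs society more or less than another. The planned total cannot carry that conclusion.

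**Working it through.** The protocol states no unit cost, no days of absence and no total, so there is no figure to reproduce. The check is to write out what each total contains under section 9.3.6.

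| Total | Hospital stays | Other resources | Transfers | Lost production | Unpaid care |
|---|---|---|---|---|---|
| Societal, all resources | DRG cost | Total cost | Included | Absent | Absent |
| Insurance, all resources | STG cost | Reimbursed cost | Included | Absent | Absent |
| Societal, AF-related | DRG cost | Total cost | Not in list | Absent | Absent |
| Insurance, AF-related | STG cost | Reimbursed cost | Not in list | Absent | Absent |

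**Step 1: what separates the two perspectives.** Both use the same resource list. They differ only in the hospital tariff (DRG or STG) and in whether the total or the reimbursed amount is taken. The step from insurance to societal therefore widens who pays for care; it adds no new kind of cost.

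**Step 2: the all-resource total.** Let T be the transfers, L lost production and U unpaid care. Taking these three components alone, the planned total differs from a societal cost by

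error = T − L − U.

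None of T, L or U appears in the protocol, so neither the size nor the sign can be worked out.

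**Step 3: the AF-related total.** Its list holds no allowances or pensions, so T drops out. What remains is the omission of L and U, again of unknown size.

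**Step 4: the comparison between drugs.** What enters the objective is the difference between arms in these errors. Matching uses a propensity score that includes age (sections 9.7.3 and 9.7.4), which should limit baseline differences. It does not equalise what follows from a stroke or bleed after the index date. The direction of any distortion in the comparison is therefore unknown for both totals.

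**Step 5: could the planned source supply the missing terms?** Section 9.4 describes reimbursed claims, including sick leave, hospital discharge summaries and death registration. It describes no wages and no carer time. The limitations in section 9.9 do not discuss the cost perspective.

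**The case against.** Four replies deserve weight.

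- *The objective concerns care related to stroke prevention in AF, and that list contains no transfers.* This is correct and narrows the point. The transfer problem belongs to the all-resource total only. The omission of lost production and unpaid care applies to both.
- *The allowances may be meant as a rough proxy for lost production.* That is possible, and removing them while keeping the societal label would leave work absence at zero. But the protocol does not describe them as a proxy, and pensions sit in the same category. This is a reason to change the label as well as the content.
- *The protocol cites the 2011 HAS guide for economic evaluations, and section 9.6 leaves details of resources and calculated variables to the SAP.* Neither document can be consulted here, and the finding does not rest on the guide's content. The components of the societal cost are not deferred, however: section 9.3.6 fixes them.
- *The allowances are a category of their own, so a reader could subtract them.* That works only if costs are tabulated by category, and it does not supply the missing terms.

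A reader might go further and infer that the societal total is too high by the amount of the transfers. The documents do not support that: the omitted components pull the other way, and none of the three is quantified. Nor can a euro amount per patient be given. The share of patients drawing allowances, the days and the daily rates would all have to be assumed, and there is no total cost to set the result against.

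**Conclusion.** The point holds as one of definition and labelling. As written, the all-resource societal total counts transfer payments, and neither that total nor the AF-related one values lost production or unpaid care. Neither is a societal cost. The net direction of the error in the all-resource total is unknown, and no size can be derived for either.

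This rests on reading section 9.3.6 literally, with the other resources taken to mean every non-hospital item in the applicable list, and on the usual health-economic convention that transfers are not resource use. The importance is low: one secondary economic objective is affected, and the clinical outcomes are not.

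**What to change.** In section 9.3.6, section 8 and the abstract:

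1. Delete sick-leave allowances, disability allowances and pensions from the first all-resource total. Keep them in the insurance perspective, where they already stand, and show them as a separate line.
2. Rename the first perspective *all-payer direct cost of reimbursed healthcare*, for both the all-resource and the AF-related totals.
3. State that lost production and unpaid care are not measured, and draw no conclusion about cost to society.

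The cost is a few lines of wording and one item removed from one total; no new data or extraction is needed. The downside is that the study no longer claims a societal perspective, which the data described in section 9.4 could not support in any case.

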9.4. DATA SOURCES

The SNIIRAM database is the national healthcare insurance system database linked to the national hospital-discharge summary database (*Programme de Médicalisation des Systèmes d'Information*, PMSI) and the national death registry, using a unique pseudonymized identifier. It includes the three main healthcare insurance funds (CNAMTS³, MSA⁴, RSI⁵), which represent about 96% of the French population, and currently some of the 19 other smaller French healthcare insurances for specific professional organisations such as militaries, deputies and senators, priests, Opera... (Moulis 2015). To the extent that the SNIIRAM is a national database, all subjects are followed-up until they died. The only dropouts are subjects who leave the country to live abroad and those who join one of the smaller French healthcare insurance organisations not yet included in the SNIIRAM, which is rare and not linked with a disease or healthcare package. The SNIIRAM contains individual pseudonymised information on (Tuppin 2010, Moulis 2015):

- General characteristics: gender, year of birth, affiliation scheme, area of residence;
- Month and year of death;
- Long-term disease (LTD, or ALD in French, and associated ICD-10 codes) with starting and ending date. There is a list of 30 LTD for a total of 3448 available ICD-10 codes, which includes most of chronic diseases with long term and/or expensive treatment; e.g. a disease such as AF is specified by the ICD-10 code within LTD. Registration with a LTD is obtained at the request of a patient's general practitioner and must be validated by the health insurance system physician. Once registered, patients receive full (i.e. 100%) reimbursement for expenditure related to the LTD, as defined by the health authorities. The LTD information is specific for the diagnosis (very low risk of false positives), but not sensitive because not all patients with the disease ask to benefit from a LTD;
- Outpatient reimbursed healthcare expenditures: visits, medical procedures, medical imageries, lab tests, drugs, medical devices, transports, sick leaves... with prescriber and professional caregiver information (medical or paramedical specialty, private/public practice), dates (prescription and dispensation), and codes (but not the medical indication nor result);
- Hospital-discharge summaries from the PMSI: ICD-10 diagnosis codes (primary, linked and associated diagnosis) for all medical, obstetric and surgery hospitalisations, with the date and duration, medical procedures and cost coding system. The hospital discharge summary includes the medical unit summaries when the patient is hospitalized successively in several medical units.

³ Caisse Nationale de l'Assurance Maladie des Travailleurs Salariés (French national health insurance fund for salaried workers)

⁴ Mutuelle Sociale Agricole (French national health insurance fund for farmers and agricultural workers)

⁵ Régime Social des Indépendants (French national health insurance fund for independent workers)

Primary diagnosis is the health problem that motivated the admission in the hospital. It is determined at hospital discharge. For patients hospitalized successively in several medical units, the primary diagnosis of the hospitalisation, as well as all medical unit primary diagnoses, are generally taken into account to define the occurrence of an outcome in a pharmacoepidemiology study.

A linked diagnosis can exist only if the primary diagnosis is a care procedure with a code Z of the ICD-10 classification (e.g. chemotherapy session) for a chronic or LTD disease. It indicates the pathology at the origin of the care procedure. Linked diagnoses can be used to define chronic diseases but are generally not taken into account to define the occurrence of an outcome in a pharmacoepidemiology study (many being false positives for the studied outcome).

Associated diagnoses are specified if they represent specific healthcare resources. They are mainly underlying chronic diseases. Associated diagnoses can be used to define chronic diseases but are generally not taken into account to define the occurrence of an outcome in a pharmacoepidemiology study (many being false positives for the studied outcome).

The CNAMTS proposes algorithms to define 56 diseases (CNAMTS 2015), including stroke and ACS. Furthermore, ICD-10 code validation in the SNIIRAM was recently published for ACS and stroke (Bezin 2015, Giroud 2015), and others validation works are on-going.

Non-hospital data are updated every month and hospital-discharge summaries yearly at end of Q3 for the previous year. Access to SNIIRAM is regulated and needs approval from Institute of Health Data (*Institut des Données de Santé - IDS*) and French data protection commission (*Commission Nationale de l'Informatique et des Libertés - CNIL*).

9.5. STUDY SIZE

The Bordeaux Pharmacoépi (BPE) has performed a previous VKA study in the EGB database, a 1/97 permanent random sample of the SNIIRAM, using similar definitions used in this protocol (Blin 2015). Between 2007 and 2011, the numbers of subjects who initiated a VKA for SPAF were 2 197 for the specific NVAF population and 3 345 for the sensitive NVAF population, which represent about 50 000 and 75 000 subjects respectively in the SNIIRAM each year, and 100 000 and 150 000 respectively for a two-year inclusion period.

Among them, the number of subjects treated with rivaroxaban, dabigatran, and VKA, as well as the number of subjects who can be matched for each comparison (rivaroxaban versus VKA, rivaroxaban versus dabigatran) will be a result of the study. Anyway, it should be clearly higher than the 7 131 and 7 133 subjects randomized in the rivaroxaban and VKA arms of the ROCKET AF trial (Patel 2011).

In the previous VKA study cited above (Blin 2015), the outcome incidence rate during VKA exposure was estimated in the specific NVAF population (with similar results for the sensitive NVAF population):

- Stroke and systemic arterial embolism: 1.6 per 100 person-years (PY), 95%CI [1.1-2.1],
- ACS: 1.6 per 100 PY, 95%CI [1.0-2.1],
- CRB: 2.6 per 100 PY, 95%CI [1.9-3.3], with 0.5 [0.3-0.9] cerebral bleeding hospitalisation, 0.8 [0.4-1.1] digestive bleeding hospitalisation, and 1.3 [0.9-1.8] other bleeding hospitalisation,
- Death: 3.5 per 100 PY, 95%CI [2.7-4.3].

Within the ranges of incidence rates of ROCKET AF trial outcomes, the following table shows the minimum hazard ratio that can be identified with a 95% confidence interval excluding 1, for the study group compared to a reference group, according to the incidence of an outcome in the reference group and the sample size for each group for analysis of matched subjects (1:1).

Minimum hazard ratio (< 1 and > 1) with a 95% confidence interval excluding 1, for the study group compared to a reference group, according to the incidence of an outcome in the reference group, sample size for each group (1:1 matching) and normal distribution

Incidence in the reference group	Hazard ratio	Sample size			
		5 000	10 000	15 000	20 000
0.5%	< 1 / >1	0.24 / 2.19	0.43 / 1.78	0.58 / 1.52	0.65 / 1.42
1.0%	< 1 / >1	0.43 / 1.78	0.58 / 1.52	0.70 / 1.35	0.75 / 1.28
1.5%	< 1 / >1	0.53 / 1.61	0.66 / 1.41	0.75 / 1.28	0.79 / 1.23
2.0%	< 1 / >1	0.59 / 1.52	0.70 / 1.35	0.78 / 1.24	0.82 / 1.20
2.5%	< 1 / >1	0.63 / 1.46	0.73 / 1.31	0.81 / 1.21	0.84 / 1.17
3.0%	< 1 / >1	0.66 / 1.41	0.75 / 1.28	0.82 / 1.19	0.89 / 1.16
4.0%	< 1 / >1	0.70 / 1.35	0.78 / 1.24	0.85 / 1.17	0.87 / 1.13
5.0%	< 1 / >1	0.73 / 1.31	0.81 / 1.21	0.86 / 1.15	0.89 / 1.12

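### Section 9.5: the detectable-hazard-ratio columns headed 15 000 and 20 000 hold values for 20 000 and 30 000 per group, and the caption omits the 90% power behind the table

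*Protocol*

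**What the plan says.** Protocol section 9.5 gives a table of hazard ratios below and above 1 for reference-group incidences from 0.5% to 5.0%. The columns are headed 5 000, 10 000, 15 000 and 20 000. The introductory sentence describes the entries as "the minimum hazard ratio that can be identified with a 95% confidence interval excluding 1, for the study group compared to a reference group", and the caption repeats this: "Minimum hazard ratio (< 1 and > 1) with a 95% confidence interval excluding 1". The entries are given "according to the incidence of an outcome in the reference group" and by "sample size for each group (1:1 matching) and normal distribution". No power is stated, and nothing indicates that the method changes from column to column.

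The same section leaves the number of matched subjects to be found in the data. It expects that number to exceed clearly the roughly 7 130 per arm of the pivotal rivaroxaban trial.

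**The concern.** Two things look wrong. First, at incidences this low the detectable hazard ratio depends almost entirely on the expected number of events, that is, group size times incidence. Cells with equal event counts should therefore agree, and in the last two columns they do not agree with the first two. Second, a hazard ratio whose 95% confidence interval just excludes 1 is a different quantity from one that is detectable with high power, and the printed values are too far from 1 to be the former.

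This table is the protocol's only quantitative statement of what the study can detect. Since matched groups well above 7 100 are expected, the right-hand columns are the ones a reader may well use. The incidences also bracket the rates the section quotes from the earlier VKA study (stroke and systemic embolism 1.6, death 3.5 per 100 person-years). A reader with 15 000 or 20 000 pairs would credit the study with more power than it has at the listed hazard ratios, and could over-read a null result.

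**Working it through.** **Inputs (all from section 9.5).** Reference incidence p₁; group size n per arm, 1:1; normal approximation; two-sided 5% level, implied by the 95% interval. Power is not stated and has to be inferred.

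**1. Check without any formula.**

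| Incidence × size | Reference events | Printed |
|---|---|---|
| 1.0% × 10 000 | 100 | 0.58 / 1.52 |
| 0.5% × 15 000 | 75 | 0.58 / 1.52 |
| 0.5% × 20 000 | 100 | 0.65 / 1.42 |
| 1.5% × 10 000 | 150 | 0.66 / 1.41 |

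The pattern is systematic. The 15 000 column at 0.5, 1.0, 1.5, 2.0 and 2.5% repeats the 10 000 column at 1.0, 2.0, 3.0, 4.0 and 5.0%. Halving the incidence and keeping the event count requires n = 20 000, not 15 000.

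**2. Reproducing the table.** With p₂ = HR × p₁, d = |p₁ − p₂| and p̄ = (p₁ + p₂)/2:

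- m = [1.96 √(2p̄(1 − p̄)) + 1.2816 √(p₁(1 − p₁) + p₂(1 − p₂))]² / d², where 1.2816 corresponds to 90% power;
- with continuity correction, n = (m/4) [1 + √(1 + 4/(m d))]².

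Upper limits in the 1.0% row:

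| Printed HR | d | m | n required | Column heading |
|---|---|---|---|---|
| 1.78 | 0.0078 | 4 732 | 4 986 | 5 000 |
| 1.52 | 0.0052 | 9 667 | 10 048 | 10 000 |
| 1.35 | 0.0035 | 19 918 | 20 486 | 15 000 |
| 1.28 | 0.0028 | 30 207 | 30 917 | 20 000 |

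Solving the same formula for HR in every cell and comparing within rounding:

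| Column heading | Values matching at the heading | Values matching at another size |
|---|---|---|
| 5 000 | 16 of 16 | – |
| 10 000 | 16 of 16 | – |
| 15 000 | 0 of 16 | 16 of 16 at 20 000 |
| 20 000 | 0 of 16 | 15 of 16 at 30 000 |

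**3. Power at the printed values and headings.** Without continuity correction, power = Φ{[d√n − 1.96 √(2p̄(1 − p̄))] / √(p₁(1 − p₁) + p₂(1 − p₂))}. This gives 90–93% in the first two columns, 79–83% in the 15 000 column and 73–78% in the 20 000 column, apart from the cell in step 4. In the 1.0% row, HR 1.35 at 15 000 has 80% and HR 1.28 at 20 000 has 75%. With sizes of 20 000 and 30 000, power returns to about 88–92%.

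**4. The single miss.** The lower limit at 3.0% and 20 000 is printed as 0.89. Down that column the values run 0.84, 0.89, 0.87, 0.89, although the lower limit must rise steadily with incidence. The formula gives 0.85 at 30 000 and 0.82 at 20 000. Power for 0.89 is 51% at 20 000 and 68% at 30 000.

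**5. The caption's literal criterion.** An observed interval that just excludes 1 corresponds to 50% power. In the 1.0% row:

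| Size | Interval just excludes 1 | Printed |
|---|---|---|
| 5 000 | 0.65 / 1.43 | 0.43 / 1.78 |
| 10 000 | 0.74 / 1.30 | 0.58 / 1.52 |
| 15 000 | 0.79 / 1.24 | 0.70 / 1.35 |
| 20 000 | 0.81 / 1.21 | 0.75 / 1.28 |

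In this row no column follows the caption.

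**The case against.** **The 90% power is inferred.** The protocol never states it, and against the only criterion it does state, every column is conservative. That is correct, so the loss of precision is relative to the standard the first two columns follow. It does not rescue the table: on the literal criterion all four columns are wrong, and the last two still disagree with the first two.

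**The 15 000 column might be 80% power at 15 000.** Taken alone it nearly fits (13 or 14 of 16 values, depending on the continuity correction). But the 20 000 column fits 80% power in only 1 or 2 of 16, and the first two columns in none of 32. This reading needs an unannounced change of power and still leaves the last column unexplained.

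**The practical effect is modest.** This stands. The study takes all eligible new users in the database, the matched number is an outcome of the study, and results will be reported as hazard ratios with 95% confidence intervals, so actual precision will be visible. The table sets no target, margin or decision rule. The limits move by roughly 0.02–0.07 below 1 and 0.02–0.10 above 1, most at 0.5% incidence, and about 80% power at 15 000 is conventional. This limits the consequences but does not make the table correct.

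**Conclusion.** The concern holds. The last two columns are not for the group sizes printed above them. By the calculation that generates the first two columns they belong to 20 000 and 30 000 per group. At the printed sizes, power for the listed hazard ratios is 79–83% and 73–78% rather than about 90%, and one cell (0.89, 51% power) fits neither reading. The caption and text misdescribe every column, because the entries are hazard ratios detectable with about 90% power.

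The mismatch between cells with equal event counts needs no assumption beyond low incidence. Identifying the sizes as 20 000 and 30 000 rests on the two-proportion normal test with 90% power and continuity correction, which is inferred from its exact fit to the first two columns. No planned estimate or analysis is affected. The error lies in the protocol's only statement of detectable effect and should be corrected before anyone relies on it.

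**What to change.** Choose one of two corrections to the table.

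- Keep the values, head the last two columns 20 000 and 30 000, and change 0.89 to 0.85.
- Keep the headings and recompute with the formula behind the first two columns:

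| Incidence | 15 000 | 20 000 |
|---|---|---|
| 0.5% | 0.53 / 1.62 | 0.58 / 1.52 |
| 1.0% | 0.65 / 1.42 | 0.70 / 1.35 |
| 1.5% | 0.71 / 1.33 | 0.75 / 1.28 |
| 2.0% | 0.75 / 1.28 | 0.78 / 1.24 |
| 2.5% | 0.78 / 1.25 | 0.81 / 1.21 |
| 3.0% | 0.80 / 1.23 | 0.82 / 1.19 |
| 4.0% | 0.82 / 1.19 | 0.85 / 1.17 |
| 5.0% | 0.84 / 1.17 | 0.86 / 1.15 |

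The continuity correction should be kept so that all four columns share one method.

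In either case, state in the text and the caption that the entries are hazard ratios detectable with 90% power at a two-sided 5% level, and name the test and the continuity correction.

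The cost is an edit to one table, its caption and one sentence. The stated precision at 15 000 and 20 000 becomes slightly less favourable; design, data and analysis are untouched.
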